7.4.1 Safety Criteria for Adjustment or Stopping Doses

7.4.1.1 SEL-212 or Placebo

A patient will be withdrawn from study drug for meeting the following stopping rule:

- sUA level < 2.0 mg/dL, measured 1 hour after the infusion of the second component of study drug is completed during Treatment Period 1

AND

- sUA level > 1.0 mg/dL measured at the Day 21 visit of Treatment Period 1 or sUA level > 6.0 mg/dL at the Day 21 visit of Treatment Periods 2, 3, 4, or 5

Stopping rules will be assessed by an independent, central, unblinded medical monitor.

If withdrawn from study drug, the patient will continue study visits to the end of Treatment Period 6. The window for all Day 21 visits is +2/-1 days.

If a Day 21 visit sUA value drawn within the protocol window is not available, but if a sUA value drawn at an unscheduled visit after the Day 21 window is available prior to dosing that is \leq 1.0 mg/dL during Treatment Period 1 or \leq 6.0 mg/dL during Treatment Periods 2, 3, 4, or 5, the patient will not be required to be withdrawn from study drug and will be eligible to receive their subsequent dose.

If 1) a Day 21 visit sUA value drawn within the protocol window is not available and no subsequent sUA results are available or 2) a Day 21 visit sUA value drawn within the protocol window is not available and a subsequent sUA drawn at an unscheduled visit after the Day 21 window is > 1.0 mg/dL during Treatment Period 1 or > 6.0 mg/dL during Treatment Periods 2, 3, 4, or 5, then the patient will be withdrawn from study drug based on the protocol deviation. If a protocol deviation occurs where a patient is not able to be dosed within the dosing day window (for example in the case of COVID-19 restrictions temporarily preventing dosing) the current treatment period will be extended up to a maximum of 90 days without skipping doses for patients with a Day 21 visit sUA value \leq 1.0 mg/dL during Treatment Period 1 or \leq 6.0 mg/dL during Treatment Periods 2, 3, 4, or 5 in the D21 visit window or subsequent up to the rescheduled dosing visit. If a protocol deviation occurs in Treatment Period 6 such that the patient was unable to have an EOS visit performed within the visit window, then the Treatment Period 6 Day 28 visit should still occur 28 days (+3/-4 days) after the Treatment Period 6 dose or as close to the visit window as possible to collect the final primary endpoint sUA sample.

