To maintain the blind, a central group of unblinded pre-specified medical personnel will adjudicate the implementation of the stopping rules.

If withdrawn from study drug, the patient will continue study visits to the end of Treatment Period 6. At the discretion of the Investigator, the patient will be permitted to return to ULT 60 days after the patient's last study drug treatment. ULT shall not be SEL-212 or any experimental or marketed uricase (e.g., rasburicase (Elitek, Fasturtec), pegloticase (Krystexxa[®])), for the remainder of the study.

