7.6.3.2 Phase 2 Studies with SEL-212

7.6.3.2.1 Phase 2 Study SEL-212/201

The Phase 2 study SEL-212/201 was designed as an open-label, ascending multiple-dose study of the combination drug, SEL-212, combined with an open-label, multiple-dose evaluation of SEL-037 (pegadricase) alone in patients with symptomatic gout and elevated blood uric acid. Part A of the study consisted of three 28-day treatment cycles of SEL-212, which was then followed by Part B, which consisted of two 28-day treatment cycles of SEL-037 alone, with a primary objective of assessing the safety, tolerability, PK, PD of SEL-212 (i.e., the combination of SEL-110 and SEL-037). Additional assessments include the ability of SEL-212 to reduce serum uric acid levels and prevent anti-drug antibodies to uricase and pegadricase. Part C of the study consisted of 5 monthly doses of SEL-212.

In Study SEL-212/201 with SEL-212, sUA levels remained consistently below 6 mg/dL in 70% to 89% of evaluable Part A patients administered SEL-212 once monthly for 3 months. The control of sUA occurred in the context of low incidences of infusion reactions, anaphylaxis, and gout flares as well as treatment-emergent adverse events (TEAEs) known to be potentially associated with rapamycin (sirolimus -

Rapamune®). Data support a once monthly dosing regimen. For cohorts 7-12 with SEL-110 doses of 0.1 mg/kg or higher, 46% of evaluable patients had sUA <6 mg/dL at week 20.

In Part C cohorts receiving 5 monthly doses of SEL-212, 61%, 71%, and 67% of eligible patients in Cohorts 13, 15, and 17, respectively, maintained sUA control (sUA, <6 mg/dL) at week 12 without the development of ADAs. All 21 patients in cohorts 13, 15 and 17 who had sUA < 6 mg/dL at week 12, maintained sUA control through the end of treatment period 5 and had sUA < 6 mg/dL at week 20.

The efficacy signal of SEL-212 in SEL-212/201 persists across multiple treatment cycles in all cohorts and through all 5 treatment cycles when SEL-212 is given at each treatment, as demonstrated by dose-dependent reductions in sUA levels below 6 mg/dL and ADA suppression in conjunction with increasing SEL-110 dose levels up to 0.15 mg/kg.

Cohorts 7,11, 13 and 17 represent the dose regimens that will be evaluated in the Phase 3 program (0.1 or 0.15 mg/kg SEL-110 and 0.2 mg/kg SEL-037). Part C cohorts 13, 15, and 17 received 5 once monthly doses of SEL-212, and patients in the proposed Phase 3 program will receive a total of 6 or 12 once monthly doses of SEL-212.

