9.2.1 Urate Lowering Therapy

Urate lowering therapy (ULT) including, but not limited to allopurinol, febuxostat (Uloric[®]), probenecid, lesinurad (Zurampic[®], Duzallo[®]), losartan, pegloticase (Krystexxa[®]) and benzbromarone ULT, **are not permitted for use during the study**. Patients will undergo a ULT washout period prior to dosing with study drug according to the schedule described in [Appendix A](#). Patients on a stable long term dose of losartan may be allowed to continue in the study without changing to another angiotensin II receptor blocker.

Patients cannot have any prior exposure to or be presently taking any experimental or marketed uricase therapy, as defined in Exclusion Criterion 19 ([Section 8.2](#)).

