10.5 Urate-Lowering Therapy Wash-out

Chronic refractory gout patients may elect to undergo wash-out of urate-lowering therapy at any point during Screening but must begin at least 7 days prior to the first dosing of study drug. Patients must continue to remain off ULT for as long as they participate in the clinical study.

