20. APPENDICES

APPENDIX A SCHEDULE OF ASSESSMENTS

Assessment	Scr. - 45 d to D0 (Pre-dose) ³	Treatment Phase														EOS ¹	ET	
		TP1 ²		TP2 ²		TP3 ²		TP4 ²		TP5 ²		TP6 ²						
		D0	D21 ⁴	D0 ⁵	D7 ⁴	D14 ⁴	D21 ⁴	D28										
Informed Consent	X																	
Demographics	X																	
Inclusion/Exclusion	X																	
Medical History	X																	
Chest X-Ray	X															X	X	
Multi-energy CT ⁶	X							X								X	X	
Physical Examinations	X ⁷	X ⁸		X ⁸		X ⁸		X ⁸		X ⁸		X ⁸				X ⁷	X ⁷	
Vital Signs	X	X ⁹		X ⁹		X ⁹		X ⁹		X ⁹		X ⁹		X	X		X	
Weight and Height ¹⁰	X		X		X		X		X		X		X		X	X	X	
12-Lead ECG	X														X		X	
Screening Labs ¹¹	X																	
COVID-19 Testing	X	As clinically indicated. Refer to Section 12.1.8.7																
Urine Pregnancy Test	X																	
Washout: ULTs	X ¹³	Patients will abstain from ULT use after the ULT washout period																
Document ULTs Discontinued	X																	
Dispense Premedication: Gout Flare and Infusion Reaction ¹²	X		X		X		X		X		X							
Premedication: Gout Flare	X ¹⁴	Continuously																
Randomization	X ¹⁵ <-----> X ¹⁵																	
Premedication: Infusion Reaction		X ¹⁶		X ¹⁶		X ¹⁶		X ¹⁶		X ¹⁶		X ¹⁶						
Safety Labs: Chemistry ¹⁷	X	X	X		X		X		X		X				X	X	X	
Safety Labs: Hematology ¹⁸	X	X	X		X		X		X		X				X	X	X	
Safety Labs: Coagulation ¹⁹	X	X	X		X		X		X		X				X	X	X	
Safety Labs: Lipids ²⁰	X	X	X		X		X		X		X				X	X	X	
Safety Labs: eGFR ¹⁷	X	X	X		X		X		X		X				X	X	X	
Blood Sample for Anti-Pegadricase ²¹		X	X	X	X	X	X	X	X	X	X	X			X	X	X	
Blood Sample for nAbs ²¹		X	X	X	X	X	X	X	X	X	X	X			X	X	X	
Blood Sample for Anti-Pegadricase POC Validation ²¹		X	X	X	X	X	X	X	X	X	X	X			X	X	X	
Blood Sample for Anti-Uricase ²¹		X	X	X	X	X	X	X	X	X	X	X			X	X	X	
Blood Sample for Biomarkers ⁶		X		X		X									X		X	
Blood Sample for Multiomic Markers		X		X		X		X		X		X			X		X	

PHASE 3 STUDY: SEL-212/302
VERSION: 7.1

EFFECTIVE DATE

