### 5.7. Protocol Deviations

All protocol deviations related to study inclusion or exclusion criteria, conduct of the trial, patient management, dosing, and sampling procedures or patient assessment will be listed. The list of protocol deviations will be reviewed by the Sponsor, the principal investigator and the study statistician, and finalized before database lock. Determination of whether the deviation is major or minor, or has impacts on primary efficacy assessment will be based on the biasing impact of the deviation on the safety and efficacy data and will be determined prior to database lock.

The use of following medications/therapies during the trial is not allowed and will be considered as major protocol deviations impacting the primary efficacy assessments:

- Uric acid lowering therapy (ULT) including, but not limited to allopurinol, febuxostat (Uloric®), probenecid, lesinurad (Zurampic®, Duzallo®), losartan, pegloticase (Krystexxa®) and benzbromarone ULT. Patients on a stable long term dose of losartan may be allowed to continue in the study without changing to another angiotensin II receptor blocker.
- The use of CYP3A4/P-gp severe inducers or CYP3A4/P-gp severe inhibitors are prohibited 14 days prior to dosing and during the trial.

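### Urate-lowering therapy that the stopping-rule section allows after withdrawal is banned elsewhere and, read literally, removes mainly SEL-212 failures from the per-protocol set

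*Protocol*

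**What the plan says.** **The permission.** Protocol 7.4.1.1, repeated in the synopsis, keeps a patient who is withdrawn from study drug on study visits to the end of Treatment Period 6 (TP6). At the investigator's discretion, "the patient will be permitted to return to ULT 60 days after the patient's last study drug treatment". SEL-212 and any uricase remain barred, so the permission covers non-uricase ULT.

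**The ban.** Protocol 9.2.1 says that ULT is "not permitted for use during the study". Protocol 10.5 says: "Patients must continue to remain off ULT for as long as they participate in the clinical study". Appendix A says: "Patients will abstain from ULT use after the ULT washout period". None of the three refers to the permission in 7.4.1.1. The SAP's own account of the stopping rules (SAP 3.3) leaves it out.

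**The analysis rule.** SAP 5.7 introduces its list, which includes ULT, with: "The use of following medications/therapies during the trial is not allowed and will be considered as major protocol deviations impacting the primary efficacy assessments". The only ULT exception there is a stable long-term dose of losartan. SAP 5.5 admits to the per-protocol set only patients free of major deviations that affect the primary efficacy assessments. SAP 5.7 also provides for deviations to be classified, by their biasing impact, before database lock.

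**The stopping rule.** Its first condition is "sUA level < 2.0 mg/dL, measured 1 hour after the infusion of the second component of study drug" in Treatment Period 1. The second is a Day 21 sUA above 1.0 mg/dL in TP1, or above 6.0 mg/dL in TP2 to TP5.

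**Use of the set.** SAP 6.1 repeats the main, second and third primary estimands on the per-protocol set. SAP 9.2 makes only the main estimand confirmatory.

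**The concern.** A patient can follow 7.4.1.1 exactly and still be recorded as a major deviator. Early withdrawal from study drug is not in itself a per-protocol exclusion: SAP 5.5 asks for one complete dose, one post-baseline sUA, an assessable endpoint and no relevant major deviation. A stopped patient who keeps attending would therefore normally stay in the set and count as a failure. The ULT rule is what takes that patient out.

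The loss is unlikely to be even across arms. Patients enter with sUA of at least 7 mg/dL and placebo is saline, so a placebo patient will hardly ever fall below 2.0 mg/dL one hour after the first infusion. Placebo non-responders who continue infusions have no ULT permission and stay in the set as failures. Removing failures mainly from the active arms raises the SEL-212 per-protocol rate, and agreement between that analysis and ITT would then reassure less than it appears to. Separately, sites hold contradictory ULT instructions within one protocol version.

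**Working it through.** **1. Planning inputs.** The plan gives no figure for ULT restart. The inputs borrowed from it are 45% response on SEL-212, 5% on placebo and about 47 patients per arm (Protocol 13.1). The underlying calculation reproduces. With two-sided alpha 2.5% and power 90%, the uncorrected size is

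n = [2.2414 × √(2 × 0.25 × 0.75) + 1.2816 × √(0.45 × 0.55 + 0.05 × 0.95)]² / 0.40² = 26.7.

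The continuity correction gives (26.7/4) × [1 + √(1 + 4/(26.7 × 0.40))]² = 31.5, so 32 per group. Then 32/0.92 = 34.8, so 35 per group, as stated. These figures are not in dispute.

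**2. Who can restart in time.** The nominal dose day in period k is 28 × (k − 1), and ULT is allowed 60 days later. TP6 runs from Day 140 to Day 168.

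| Last dose in | Dose day | ULT allowed from | Relative to TP6 |
|---|---|---|---|
| TP1 | 0 | 60 | before |
| TP2 | 28 | 88 | before |
| TP3 | 56 | 116 | before |
| TP4 | 84 | 144 | during |
| TP5 | 112 | 172 | after |

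Only patients last dosed in TP1 to TP4 are affected.

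**3. How many that might be (assumption).** Protocol 7.6.3.2.1 reports that "61%, 71%, and 67% of eligible patients in Cohorts 13, 15, and 17, respectively, maintained sUA control" at week 12. Cohorts 13 and 17 used Phase 3 dose regimens, with 61% and 67% controlled. It adds: "All 21 patients in cohorts 13, 15 and 17 who had sUA < 6 mg/dL at week 12, maintained sUA control", through to week 20. Losses in those cohorts were therefore early. Carried over to 47 per arm:

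- 47 × (1 − 0.67) = 15.5
- 47 × (1 − 0.61) = 18.3

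That is about 16 to 18 early losses per SEL-212 arm.

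**4. Effect on the per-protocol rate.** Responders: 47 × 0.45 = 21.15, taken as 21, so the starting rate is 21/47 = 44.7%. The restart rates are assumptions; the documents give none. Every patient removed is taken to be a SEL-212 failure, and no other exclusion is modelled.

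| Restart rate | Removed | Per-protocol rate |
|---|---|---|
| 10% of 15.5 | 1.55 | 21/45.45 = 46.2% |
| 10% of 18.3 | 1.83 | 21/45.17 = 46.5% |
| 25% of 15.5 | 3.88 | 21/43.12 = 48.7% |
| 25% of 18.3 | 4.58 | 21/42.42 = 49.5% |

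Keeping 21.15 unrounded adds 0.3 to 0.4 points to each rate.

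**5. Direction by estimand.**

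- Main: meeting the stopping rule is a composite failure, so removal raises the SEL-212 rate.
- Third: every listed event is a failure, so the direction is the same.
- Second: TP6 sUA is used even after discontinuation. A stopped patient whose sUA falls below 6 mg/dL on ULT could be a responder, and removing that patient would lower the SEL-212 rate. The direction is uncertain.

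**The case against.** The strongest reply is that ULT taken as 7.4.1.1 allows is authorised conduct and so arguably no deviation, and that the review before database lock can settle it. This stands in part: exclusion is the literal reading and not a certainty. But SAP 5.7 lists ULT categorically, names losartan as the only exception, and never mentions 7.4.1.1. A foreseeable case should not be left to discretion.

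Second, removing patients whose TP6 sUA is confounded by another drug is an ordinary purpose of a per-protocol set. That is fair for the second estimand. It does not help the main and third, where a stopping-rule patient is a failure whatever the later sUA.

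Third, the size is conjecture. This stands. Loss of sUA below 6 mg/dL at week 12 is not the same event as the Phase 3 rule, which stops at 1.0 mg/dL in TP1, and the documents do not say that the Phase 2 cohorts used that rule.

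Fourth, no decision turns on it. With illustrative counts, a continuity-corrected chi-square test gives p of about 0.00002 for 21/47 against 2/47, and about 0.000004 for 21/43 against 2/47. The conclusion is the same. What suffers is the value of the supportive analysis as a check.

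A reader might infer a larger effect by letting any of the 26 failures per arm (47 − 21) restart. Then 10% and 25% would remove 2.6 and 6.5 patients, giving 21/44.4 = 47.3% and 21/40.5 = 51.9%, or 42 to 47 points over placebo. The timing does not support that base, since TP5 stops cannot qualify. Against 15.5 to 18.3 eligible patients, those removals need 14% to 17% and 35% to 42% of them to restart.

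**Conclusion.** The contradiction in the text is established. The per-protocol consequence follows from a literal reading of SAP 5.5 and 5.7 and would probably favour SEL-212 in the main and third primary estimands on that set. Under the stated assumptions the shift is from about 45% to about 46% to 49% (49.5% at the top of the table); the true size is unknown.

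The word 'mainly' matters. The permission covers any withdrawal from study drug, so adverse events, COVID-19 or a missing Day 21 sUA could take out some placebo patients too.

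Two stronger readings are tempting and unsupported. One is that all three repeated primary estimands are biased toward SEL-212; the second may go either way. The other is that the confirmatory result is at risk. On ITT, stopping-rule patients are composite failures with or without ULT, and the mITT and all-randomized sets do not exclude for ULT use.

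One narrow gap does reach the main estimand. A patient withdrawn for a missing Day 21 sUA is not named among the composite failures, and SAP 6.1 does not say whether ULT taken under 7.4.1.1 is prohibited medication.

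Severity: minor.

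**What to change.** 1. Cross-reference the 7.4.1.1 exception in Protocol 9.2.1, 10.5 and Appendix A, and in SAP 5.7.
2. State in SAP 5.5 and 5.7 that ULT started after withdrawal from study drug, as 7.4.1.1 permits, is not by itself a per-protocol exclusion for the main and third primary estimands, where stopping-rule patients stay in as failures. Leave the per-protocol handling of the second estimand to the sponsor, and record the choice before unblinding.
3. State in SAP 6.1 that such ULT still counts as sUA-lowering medication under the composite strategy. This closes the gap for patients withdrawn for a missing Day 21 sUA.

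The cost is wording in the two documents; no new data are needed. The SEL-212 per-protocol rate may come out lower than under the literal rule. If the sponsor keeps ULT users in the set for the second estimand, ULT-affected sUA values enter that analysis; if it removes them, a separate per-protocol flag is needed for that estimand.

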7.4.2 Criteria for Adjustment or Stopping Doses

An independent Data and Safety Monitoring Board (DSMB) will be formed by charter to assist in reviewing safety data and may provide recommendations to the Sponsor regarding study drug dose adjustment or study termination.

7.5 Criteria for Study Termination

The study can be terminated at any time at the Sponsor's sole discretion. Otherwise, the study will be terminated when all patients have completed follow-up assessments ([Appendix A](#)) or the Sponsor or regulatory agency(ies) have determined there is an unacceptable risk to patients or additional dosing or procedures are not warranted or necessary.

The study may be terminated at a particular investigational site under the following conditions:

- The Investigator fails to enroll patients at an acceptable rate;
- The Investigator fails to comply with pertinent regulations;
- There is insufficient adherence (i.e., compliance) to the protocol;
- Knowingly false information is submitted to the IRB/IEC, Sponsor or designee, or regulatory authorities.

7.6 Study Rationale

7.6.1 Rationale for the Study Design

Refractory gout is a serious condition affecting approximately >200,000 patients in the United States and is characterized by uric acid levels that are not adequately controlled by xanthine oxidase inhibitors, such as allopurinol or febuxostat, or for whom such drugs are contraindicated. About 5% to 10% of gout patients are not treated effectively with allopurinol and thus continue to have acute flares and may experience destructive joint damage and tophus formation ([Edwards 2008](#), [Fels 2008](#)). Additionally, approximately 2% of gout patients exposed develop hypersensitivity to allopurinol which can lead to very serious complications and even death ([Markel 2005](#)).

Pegloticase (Krystexxa[®]), a pegylated uricase, was approved by the United States Food and Drug Administration (FDA) in 2010 for the treatment of chronic gout in patients refractory to conventional therapy. Pegloticase is effective in lowering serum uric acid after a single dose. However, >58% of subjects treated with pegloticase experience loss of efficacy within 6 months with the vast majority experiencing loss of efficacy within 3 months due to the formation of anti-drug antibodies (ADAs) with the possibility of infusion reactions, sometimes severe.

SEL-212 is a combination drug product consisting of SEL-037 and SEL-110.36. SEL-037 (pegadricase, pegylated recombinant *Candida utilis* urate oxidase) is an investigational biological therapeutic product presented as a lyophilized pegylated recombinant uricase for intravenous injection. SEL-110.36 is designed to inhibit the formation of ADAs when concomitantly administered with a biologic, specifically, the uricase, pegadricase or SEL-037.

The overall development of SEL-212 remains focused on mitigating the formation of ADAs with the goal of providing a product with better efficacy and safety profiles in patients than the only approved available therapy.

Study SEL-212/302 is a randomized, double-blind, placebo-controlled, parallel-arm study to determine the safety and efficacy of multiple doses of SEL-212 compared to placebo.

A randomized, controlled study is the gold-standard for evaluation of efficacy in clinical research. Randomized, controlled studies are quantitative, comparative, controlled experiments in which treatment effect sizes may be determined with less bias than observational trials. Randomization is considered the most powerful experimental design in clinical trials: with other variables equal between groups, on average, any differences in outcome can be attributed to the intervention.

The blinding scheme in this study will be applied to all patients, Investigators, study personnel, and Sponsor personnel involved in the conduct of the study, except for a designated unblinded statistician who will generate and have access to the randomization codes, a designated unblinded site representative (e.g., pharmacist) who will prepare study drug on the day of treatment, an unblinded infusion nurse who will be responsible for dosing the patient, a designated unblinded medical monitor for assessing the treatment stopping rules, and unblinded drug supply personnel. Blinding and randomization will reduce the potential for treatment bias and will improve the veracity of detected efficacy and safety signals, particularly in the use of patient-reported quality of life assessments. The parallel arms involving active treatment and placebo will permit adequate statistical comparison of the groups for efficacy and safety signal detection.

Placebo (normal saline) rather than an active control will be employed in this study for ethical and practical considerations. The approved therapeutic for patients with gout refractory to conventional therapy (pegloticase) and the uricase product currently used to treat hyperuricemia (rasburicase) include exogenous enzymes that are highly immunogenic ([Section 5.5](#)) and that would expose patients randomized to an active control group to unnecessary risk. The dosing regimens of the approved enzymes are substantially different from the dosing regimen of SEL-212 and would defeat the steps taken to blind the study. The use of multiple doses of SEL-212 will help determine optimal efficacy: safety profile in a heterogenous population of patients with significant co-morbidities.

